
Additionally, some women contacted the Native Sister to learn more about the study. The Native Sister shared the woman's name and phone number with the research coordinator who then contacted the woman to describe the study and enroll her if she is interested.

Other methods of recruitment included posting flyers throughout Bethel. These posters were the same design as the approved posters already being displayed at YKHC listing the 16 villages in the study. Facebook was found to be an effective method of recruitment for Phase I. In fact, we chose to implement Facebook recruitment for the Phase I individual interviews after initial advice from community members who participated in our Phase I focus groups. Therefore, during Phase II we posted study information on Facebook pages for the study villages. Each village has its own Facebook page and thus the risk of control participants learning about intervention aspects such as Native Sisters would be minimal. To enhance recruitment, generic study postcards were mailed to all households in the 8 control villages to ensure community members learn about the study. The postcards were mailed in a box from Mayo Clinic to YKHC Bethel to be postmarked then sent to each village post office for distribution.

We chose to limit enrollment to females aged 18 years and older as different individual-based interventions and age-appropriate assessments may be needed for adolescent tobacco users given their differing development and cognitive abilities. Only about 7% of pregnancies in the region are among girls <17 years of age. About 95% of Y-K Delta residents have access to a telephone in their home. Baseline tobacco users as

well as non-users were eligible to focus on prevention and cessation of tobacco during pregnancy and the postpartum period. Tobacco use status will be biochemically confirmed at baseline using saliva cotinine.

Consent process:

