Treatment Self-regulation Questionnaire (TSRQ) (intrinsic vs. extrinsic motivation for change) (156,157)		15	X	✗	X	X	X
Yupik Wellness Questionnaire (i.e., positive cultural activities) (101)		24	X	✗	X	X	X
Perceived Stress Scale (158) and CES-D Depression Scale (159)		4/20	X	✗	X	X	X
Prenatal care utilization (161)		2	X	✗	X		

To reduce participant burden, the week 12 pregnancy assessment was reduced to only one form (program evaluation). No questions were added. We noted early in the follow-up phase that the week 12 assessment was not feasible to complete at the intended time frame. This is because most women enrolled at ≥ 24 weeks gestation, in which case the week 36 assessment coincides with the 12 week post-enrollment assessment. Of 352 participants enrolled, 222 (63%) were ≥ 24 weeks gestation at enrollment. Moreover, only 9% of women (33/352) enrolled before 12 weeks gestation. The consent form acknowledges that the week 12 assessment would be conducted depending on when they enroll in the study. To accommodate varying enrollment/assessment schedules and to standardize the assessment process for research staff and participants, we will ask the week 12 program evaluation questions at the week 36 assessment, and participants will receive a gift card for completing each of these assessments. Thus, the potential number of gift cards provided and assessments conducted with participants will remain the same.

Intervention (Intervention Villages only):

Native Sister Intervention Components

Native Sister hiring and training:

Native Sisters were hired by YKHC as a sub-contracted employee. The Native Sister's role is one of a study ambassador for the Healthy Pregnancies Study in their village. Native Sisters must meet the following qualifications:

- Be considered an Elder: 55 years and older or someone who is younger but who is seen as credible in the community/or as a leader
- Speak both English and Yup'ik
- Tobacco-free (no tobacco use in the last 6 months)
- Believe that no tobacco use is safe when a woman is pregnant

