For intervention villages, we will assess the pregnant woman's reported exposure to the social marketing campaign using continuous scales adapted from prior research. For example, her awareness/recall of the campaign messages and media (e.g., point of purchase displays), if she used/read various campaign media such as brochures and viewed the digital stories DVD, and if she shared these materials and/or the information with others in her village. An intervention exposure index will be created based on item responses to permit exploration of dose response effects.

De-identified data will be obtained from the YKDRH on the total number of positive pregnancy tests in each randomized village during the recruitment period. The study staff will track recruitment data, completion of each follow-up assessment among enrolled participants and use of NRT/other treatments.

To inform dissemination efforts, we will track and summarize the cost of intervention components including time spent by the Native Sisters and program materials displayed/distributed in each village. We will exclude development costs, as these would not be considered in disseminating the intervention.

Dissemination Plan To communicate and introduce the study to the local community we submitted a story to the region-specific "Tundra Drums" newspaper and locally owned radio stations (KYKD, KYUK). Dissemination of the results will occur after each phase of the project with guidance from our CAC. The first level of dissemination will be to the YKHC Human Studies Committee and Board. After receiving approvals, the second level of dissemination will be to the local community by submitting a story to local newspapers, locally owned radio stations, and the YKHC employee website. A booklet or brochure and a power point presentation with key project findings will be developed and approved by the YKHC. Presentations will be given to community members at local gatherings in Bethel and to YKDRH providers. The YKHC staff will also travel to the study villages to provide promotional items from the campaign, along with the brochures and DVD digital stories. They will meet with village councils to share results as feasible.

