up or who do not provide biochemical confirmation classified as using tobacco. The analysis will be supplemented with multiple imputation methods to classify lost to follow-up as tobacco users or non-users. GEE will also be used to examine condition differences on the point prevalence tobacco use rates at 12 weeks/week 36 gestation, and at 8 weeks postpartum. Because only 14 df are available for the test of the intervention we will employ a small sample correction to the standard GEE. For these analyses, the stratification factor (village size) will be adjusted for in the analysis. Based on the biochemically confirmed tobacco use status at baseline, in an exploratory fashion we will examine potential treatment effects separately among baseline non-tobacco users and tobacco users respectively using GEE. Within intervention villages only, exposure dose will be tested as a predictor of tobacco use at 36 weeks gestation and 6 months postpartum using GEE. A similar analysis will be performed using the intervention implementation index to examine potential dose response effects. Assuming an ICC of 0.01 and an effective sample size of 135 subjects in the intervention arm after correction for the ICC, there will be 80% power to detect an effect size of at least 0.5 standard deviation units when examining the association of intervention exposure (i.e., continuous measure) and abstinence rates. Potential village differences on intervention exposure or implementation will be summarized graphically and compared using GEE. The percentage of enrolled participants who complete 6- month follow-up postpartum (retention) will be compared between intervention and control villages using GEE.

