We will follow procedures suggested by MacKinnon to assess mediation (**Aim 2**), fitting three GEE models to the data. We will first estimate the intervention effect separately for the dependent variable (with regression adjustment for covariates). That model provides an estimate of the total effect of the intervention, which MacKinnon labels C. Next we will estimate the intervention effect for each mediator (with regression adjustment for covariates); that model provides an estimate of the effect of the intervention on the mediator, which MacKinnon labels A. Finally we will estimate the mediated intervention effect for the dependent variable by adjusting for the mediator (and covariates); that model provides an estimate of the unmediated (i.e., direct) intervention effect, which MacKinnon labels C, and the intervention-adjusted effect of the mediator on the dependent variable, which MacKinnon labels B. Assuming an ICC of 0.01 and an effective sample size of 270 subjects after correction for the ICC, there will be 80% power to detect an effect size of at least 0.35 standard deviation units for paths A and B assuming a two-sided, alpha=0.05 test at 6-months postpartum.

Treatment condition differences on changes in other variables targeted (see Table 4) will be examined using GEE with a logit (binomial outcome) or identify (continuous outcome) links as appropriate.

We will summarize the cost of the program per pregnant woman enrolled (reached) along with cost per woman abstinent from tobacco at 6 months postpartum follow-up using descriptive statistics.

Endpoints

Primary:

Biochemically confirmed tobacco abstinence at 6-months post-partum.

Secondary:

Biochemically confirmed tobacco abstinence at end of pregnancy. Also, changes in proposed theory-based mediators of intervention efficacy.

Project Timeline

We have received approval from NIH to extend out the study timeline from 5 to 6 years total. We are currently beginning the 5th year of our 6-year NIH grant. Table 4 shows the timeline for the remaining Phase II

activities. We will request from NIH a 7th project year as a no-cost extension to complete analyses and dissemination if necessary and long as remaining funds permit.

Table 4

PROJECT TIMELINE, YEARS 3-7,
Dates: May 1, 2015 – April 30, 2020

Activity	Year 3 2015-2016				Year 4 2016-2017				Year 5 2017-2018				Year 6 2018-2019				Year 7 2019-2020 No Cost Extension					

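### The two exploratory dose-response models test a non-randomised dose with no baseline covariate, so baseline differences between women can appear as a dose effect or hide one

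*Combined protocol and SAP*

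**What the plan says.** The Phase II Data Analysis Plan sets up two models in the intervention arm.

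- **Exposure dose:** "Within intervention villages only, exposure dose will be tested as a predictor of tobacco use at 36 weeks gestation and 6 months postpartum using GEE".
- **Implementation:** "A similar analysis will be performed using the intervention implementation index to examine potential dose response effects".

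The first appears to use the index described under Program Evaluation, which is built from what a woman reports having seen, used and shared of the campaign: "An intervention exposure index will be created based on item responses to permit exploration of dose response effects". The second index comes from the Native Sisters checklist (Data Management and Quality Assurance). That checklist records sessions completed out of six, as well as media distributed, presentations and attendance.

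The nearest statement on adjustment is "For these analyses, the stratification factor (village size) will be adjusted for in the analysis". It stands before the dose models and directly after the comparisons between conditions. Baseline tobacco status appears in the same paragraph only for subgroup treatment effects: "in an exploratory fashion we will examine potential treatment effects separately among baseline non-tobacco users and tobacco users respectively using GEE". The mediation models are adjusted for covariates that are not listed, and that text does not extend to the dose models. No Phase II analysis names gestation at enrolment as a covariate.

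Baseline status is available: "Tobacco use status will be biochemically confirmed at baseline using saliva cotinine". Gestation at enrolment is known too: "Of 352 participants enrolled, 222 (63%) were ≥ 24 weeks gestation at enrollment".

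**The concern.** Randomising villages balances the two conditions. It does not balance women with high and low exposure inside the intervention arm. The trial enrols both users and non-users of tobacco, and status at enrolment is an obvious candidate to predict status later. This holds most for week 36, which for 63% of women falls at most 12 weeks after enrolment. If the two groups also differ in recall of the campaign, or in sessions completed, the unadjusted coefficient mixes that difference with any effect of dose.

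The mixing can go either way. More exposure among baseline non-users would create or inflate an apparent benefit of dose. More exposure among baseline users would hide a real one.

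The trial has no campaign-only arm. The section Rationale for a 2-Arm Design relies on a process evaluation of exposure in view of the intervention's complexity, so a positive dose result could carry weight in interpretation.

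**Working it through.** **1. The plan's own figure.** The Data Analysis Plan gives an effective sample of 135 and 80% power at 0.5 SD. With 320 women there are 160 per arm, at 20 per village and ICC 0.01:

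160 / (1 + 19 × 0.01) = 160 / 1.19 = 134.5, that is 135.

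The Power Statement assumes 55% tobacco use at 6 months in the intervention arm, so 45% are abstinent. Compare mean dose between abstainers (0.45 × 135 = 60.75) and users (74.25), with a two-sided 0.05 test. That is an assumption here, because no level is stated for these models.

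- SE = √(1/60.75 + 1/74.25) = 0.173 SD
- Detectable difference at 80% power = (1.96 + 0.842) × 0.173 = 0.485 SD
- Power at 0.5 SD = Φ(0.5/0.173 − 1.96) = 82%

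The stated figure is reproduced. At week 36 (65% use) the same steps give 79% power.

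**2. Spurious difference when dose has no effect.** Let q be the share of baseline non-users, a₀ and a₁ the abstinence rates in baseline non-users and users, and g the extra dose of non-users in SD. Then

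spurious difference = g × [q·a₀/A − q(1 − a₀)/(1 − A)], with A = q·a₀ + (1 − q)·a₁.

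The documents give none of q, a₀, a₁ or g, so the values below are assumptions.

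*Large contrast:* q = 0.25, a₀ = 80%, a₁ = 33% (47 points).
- A = 0.20 + 0.2475 = 0.4475
- Share of non-users among abstainers = 0.20/0.4475 = 0.447; among tobacco users = 0.05/0.5525 = 0.090
- Difference in shares = 0.356, so g = 0.5 gives 0.18 SD and g = 1.0 gives 0.36 SD

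*Weaker contrast:* q = 0.25, 60% v 40% (20 points).
- A = 0.45; shares 0.333 and 0.182; difference 0.152, so g = 0.5 gives 0.08 SD

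*Pilot-sized contrast:* the Power Statement gives 400 women who used tobacco before pregnancy, with 17% quitting in pregnancy, 63% of quitters relapsing and 69% of all 400 using at 6 weeks postpartum.
- Quitters: 0.17 × 400 = 68, of whom 0.63 × 68 = 43 were using
- All users at 6 weeks: 0.69 × 400 = 276
- Continuing users: (276 − 43)/332 = 70%
- Gap: 70% − 63% = 7 points. Even with g = 1.0 this gives at most about 0.06 SD at 6 months.

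**3. False-positive rates.** These come from logistic simulation with n = 135, two-sided 0.05 and no true dose effect; the 7-point row uses a closed-form normal approximation.

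| Outcome gap by baseline status | Dose gap | Unadjusted | Baseline status in model |
|---|---|---|---|
| 7 points | 0.5 SD | about 5% | not run |
| 20 points | 0.5 SD | about 6-7% | about 5% |
| 47 points | 0.5 SD | about 16-17% | about 5% |
| 47 points | 1.0 SD | about 45% | about 5% |

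The last column is near 5% by construction, because the only confounder simulated is the one adjusted for.

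**4. Cost in power.** If the added covariates explain a share R² of dose (assumed), the effective sample becomes 135 × (1 − R²). At R² = 0.10 it is 121.5, SE = 0.173/√0.9 = 0.182, and power at 0.5 SD is Φ(0.5/0.182 − 1.96) = 78%, against 82% unadjusted. At R² = 0.30 it is 68%. Any gain from covariates that predict the outcome is ignored.

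**5. Gestation.** Figure 1 places the prenatal sessions 1, 2 and 4 weeks after enrolment. A woman enrolled at 24 weeks is due to finish them by week 28. Only a woman enrolled after week 32 (36 − 4) has a scheduled prenatal session after week 36, and the documents do not say how many such women there are.

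**The case against.** The strongest reply is that these analyses are exploratory. The protocol says both indices exist to explore dose response, the power sentence already speaks of an association, and the primary comparison rests on randomisation. All of this stands and limits the weight of the point. It does not supply the missing covariate.

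The reply on size also has force. The closest pilot figures show a gap of about 7 points between prenatal quitters and continuing users, and almost none by pre-pregnancy status (69% v 70%). But the data are from 6 weeks postpartum, no cotinine confirmation is described, and neither grouping is status at enrolment. They do not support 47 points and do not exclude a large gap, particularly at week 36.

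A reader might infer four stronger things that the documents do not support:

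- *That both models are distorted by who takes up the sessions.* Session counts enter only through the implementation index, which also holds delivery measures such as media distributed. The first model concerns reported campaign exposure.
- *That late enrolment is a demonstrated confounder.* The 63% figure does not show a shortened dose (step 5), and nothing says that gestation predicts tobacco use. It is a candidate only.
- *That the error always favours the programme.* The direction depends on which group is more exposed.
- *That dissemination would rest on this result.* No section makes it depend on dose response.

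**Conclusion.** The omission is real. Followed as written, either model can report a baseline difference as a dose response or conceal a true one. The size cannot be fixed from the documents. The unadjusted false-positive rate ranges from about 5-7% to about 45% across the assumed settings. The upper values need both a large outcome gap and a dose gap of 0.5 to 1.0 SD, so they are scenarios and not expectations. The point concerns exploratory analyses and leaves the randomised primary result untouched. It is worth correcting because the main covariate is already collected.

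Adjustment would not make the estimate causal. Motivation remains. So does the rule that counts missing outcomes as tobacco use, if it carries over to these models: with an assumed 20% missing and 1 SD less dose among them, it alone gives about 0.34 SD and about 50% false positives at 6 months.

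**What to change.** In both dose-response GEEs, for both time points:

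1. Include baseline cotinine-confirmed tobacco status and the village-size stratum.
2. Add gestational age at enrolment as a candidate confounder, mainly for the week 36 outcome.
3. Make the adjusted coefficient the reported result.
4. Describe it as an association that may still be confounded by motivation and by counting missing outcomes as tobacco use.

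This changes SAP wording only and needs no new data. It uses a few degrees of freedom in an arm of eight villages. Power at 0.5 SD falls from about 82% to about 78% if the covariates explain 10% of dose, and further if they explain more. Adjusting for status at enrolment may also remove any campaign effect that occurred before a woman enrolled, and the report should say so.

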In Phase II, we will conduct an evaluation of the intervention applying a group-randomized design with village as the unit of assignment. Sixteen villages were selected and randomly assigned to receive the intervention (8 villages) or control condition (8 villages) with ≥ 22 pregnant women recruited per village.

Subject population:

Sample size calculation. We estimate recruiting ≥ 22 pregnant women per village (N=352). Accounting for an estimated attrition rate of 10% due to miscarriage, abortion or fetal demise, we plan to achieve a final sample of at least 320 women eligible for follow-up. All pregnant women (tobacco users and non-users) will be eligible for enrollment.

Actual accrual. We met our targeted sample size of 352 women enrolled. Encouragingly, overall participation from control villages (n=164) was similar to overall participation from intervention villages (n=188). Although we estimated 22 or more women enrolled in each village, this was not feasible. Study villages were more or less interested in participating, with a range of 2 to 42 women enrolled in the 16 study villages.

Inclusion Criteria:

Participants consist of 352 Alaska Native pregnant adults age 18 and older. To be eligible for the study, Alaska Native pregnant women participants must:

- Be 18 years of age or older
- Provide written informed consent
- Currently 36 weeks or less gestation
- Access to a working telephone

Exclusion Criteria:

Individuals will be considered ineligible to participate in the study if they are:

- Not Alaska Native
- Under the age of 18
- Currently not pregnant or ≥ 37 weeks gestation
- No access to a working telephone
- Refuse to provide written informed consent

Will a Certificate of Confidentiality be obtained? If yes, provide an explanation.

No, a Certificate of Confidentiality will not be obtained.

Study Design

Methods: *Describe, in detail, the research activities that will be conducted under this protocol:*

Phase IA. Social Marketing Campaign Development

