Please note that the materials above were informed by the focus groups and individual interviews conducted among community members in the completed Phase I work. Specifically, participants preferred a fact-based approach that grabbed the attention from community members.

Data Management and Quality Assurance:

We will use the same coordination and communication procedures successfully utilized in our previous work including a weekly study team meeting held via teleconference. [name] and Mayo Clinic study staff provided training to the research coordinator on the study protocol on-site in Bethel.

All original participant forms are maintained in a locked file at the Healthy Pregnancies YKHC office. These forms with the exception of enrollment forms contain a study ID number only (e.g., no names or other identifying information). YKHC and Mayo Clinic study staff share the workload for assessments. For some period of time, a YKHC research coordinator was not hired and thus the program managers overseeing the project requested Mayo research staff to assist. The study staff from Mayo Clinic were added to the consent form as personnel modifications approved by the YKHC HSC as well as Mayo Clinic and Alaska Area IRB. The consent form allows for data sharing between Mayo Clinic and YKHC. An electronic data-tracking sheet with names and contact information is shared between Mayo and YKHC using a secure, encrypted email transfer.

When assessments are completed by YKHC, electronic (scanned) copies are transferred to Mayo Clinic Division of Biostatistics via secure encrypted email and stored on a secure server. Mayo Clinic staff enters data

into a secure REDCap (Research Electronic Data Capture) database that contains only the Study ID. Access to the information is restricted to the study statistician, [name], and study staff only. We will monitor quality control of the data through review of participant forms and procedures on-site in Bethel. Moreover, the biostatistician, [name], will perform monthly data checks and will also analyze the data. At both YKHC and Mayo Clinic, standard data security and monitoring procedures are in place. From the daily Native Sisters checklist, an implementation index has been created to permit exploration of dose response effects.

Program Evaluation:

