who quit tobacco use during pregnancy, the relapse rate was 63% at 6 weeks postpartum. Of the 432 women reporting no tobacco use in the three months before pregnancy, 75% reported tobacco use during the prenatal period, and 70% at 6 weeks postpartum. Alaska PRAMS data indicate similar cessation rates during pregnancy (20%) and rates of relapse postpartum (57%) in the southwest region. During the time periods these estimates were obtained, women received the same standard of care as in the proposed study. Therefore, we do not expect our usual care condition to impact tobacco use beyond the natural history of tobacco use in pregnancy. The Clinical Practice Guideline meta-analysis found that behavioral/psychosocial interventions for pregnant smokers were associated with an abstinence rate of 13% in late pregnancy vs. 7% for control conditions (OR= 1.8, 95% CI 1.5-2.3). We do not have guidance from the literature on the possible impact of interventions for baseline non-tobacco users but would expect greater impact in this group compared to those already using tobacco. Accordingly, we estimate the rate of tobacco use at 6 months postpartum to be 70% in our control villages and 55% in the intervention villages (estimated odds ratio 1.91) and in late pregnancy to be 80% vs. 65% with an odds ratio of 2.15. A difference of 15% would be of clinical significance in terms of the potential to impact the current standard of care at the YKDRH.

Estimates of intra-class correlations (ICC) within communities are quite modest, e.g., ranging from 0.002 to 0.012 for a variety of survey variables included in the Minnesota Heart Health Program. For the proportion currently smoking the estimated ICC was 0.00272. Other literature indicates that in community based trials using group-randomized designs (e.g., NCI Working Well Trial) the ICC ranged from 0.01-0.03 for the four outcome variables at baseline. Lumley et al. reviewed 9 cluster randomized trials of prenatal cessation interventions but most did not report the ICC and/or account for the clustering effect in the analysis. Table 3 (below) provides power estimates for the estimated outcomes with 16 villages total, average village participant size of 20 (total sample size = 320), and with varying ICC estimates. With an ICC of 0.01 we will have >80% power to detect the hypothesized differences between conditions at 6 months postpartum.

Table 3. Power estimates for 1-sided alpha=0.05 test

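### The within-intervention dose-response GEEs rest on eight villages, but the plan states no small-sample correction for them and its power figure ignores the number of clusters

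*Combined protocol and SAP*

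**What the plan says.** All of the following is in Statistical Considerations, Phase II, unless another place is named.

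- **Correction.** The Data Analysis Plan says: "Because only 14 df are available for the test of the intervention we will employ a small sample correction to the standard GEE". The 14 df come from 16 villages less two arms.
- **Exposure test.** Later in the same paragraph: "Within intervention villages only, exposure dose will be tested as a predictor of tobacco use at 36 weeks gestation and 6 months postpartum using GEE".
- **Implementation test.** "A similar analysis will be performed using the intervention implementation index to examine potential dose response effects". Data Management and Quality Assurance gives the source of this index: "From the daily Native Sisters checklist, an implementation index has been created to permit exploration of dose response effects".
- **Power.** "Assuming an ICC of 0.01 and an effective sample size of 135 subjects in the intervention arm after correction for the ICC", the plan claims that "there will be 80% power to detect an effect size of at least 0.5 standard deviation units when examining the association of intervention exposure". No alpha or sidedness is attached to that sentence.
- **Clusters.** The Phase II accrual section has villages "randomly assigned to receive the intervention (8 villages) or control condition (8 villages) with ≥ 22 pregnant women recruited per village", so the dose-response models have eight clusters.

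The dose-response sentences name GEE and nothing more. They give no variance estimator, working correlation or reference distribution.

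**The concern.** A sandwich variance estimated from eight clusters is biased downwards on average, and a normal reference is too narrow for it. The plan recognises this for the arm comparison with 16 villages. The dose-response models have half as many, yet the correction is not stated for them. An intercept and one predictor leave 8 − 2 = 6 df, or 5 if village size is also fitted.

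The implementation index is the more exposed of the two. Part of its checklist (media handed out, presentations, attendance) describes a village. To that extent the index takes eight values, however many women are in the model.

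At stake is how a dose-response result is read. Without a correction, a chance association is declared too often. With one, a null result would be set against a power figure that makes no allowance for eight clusters.

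**Working it through.** **Inputs from the plan.** Eight intervention villages; an average of 20 women each (Power Statement: "average village participant size of 20 (total sample size = 320), and with varying ICC estimates"), so 160 women; ICC 0.01 for the power figure, with 0.01–0.03 cited from earlier trials; intervention-arm abstinence of 45% at 6 months postpartum (100 − 55) and 35% in late pregnancy (100 − 65). I read 0.5 SD as the difference in mean exposure between abstinent and tobacco-using women.

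**1. Reproduce the plan's figure.**
- Design effect: 1 + 19 × 0.01 = 1.19. Effective n: 160 / 1.19 = 134.5, i.e. the stated 135.
- Detectable effect at 80% power, two-sided 0.05, normal reference: (1.960 + 0.842) / √(n·p·(1 − p)).
  - p = 0.45: 2.802 / √(135 × 0.2475) = 2.802 / 5.780 = 0.485 SD.
  - p = 0.35: 2.802 / √(135 × 0.2275) = 2.802 / 5.542 = 0.506 SD.
- Both round to 0.5. Power at exactly 0.5 SD is 82% and 79%.
- One-sided 0.05 with a normal reference gives 87–90% at 0.5 SD, which does not match the plan.
- The mediation power statement (effective n 270, 0.35 SD) is explicitly two-sided. The same formula gives 2.802 / √(270 × 0.2475) = 0.343, consistent with it.

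So the 80% is most likely a two-sided normal calculation that adjusts n for the ICC but not the reference distribution for eight clusters.

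**2. Power with a 6-df reference.** The noncentrality is 0.5 × 5.780 = 2.890 (p = 0.45) or 0.5 × 5.542 = 2.771 (p = 0.35). The two-sided critical value rises from 1.960 to 2.447.

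| Power at 0.5 SD, effective n 135 | 50/50 | 45/55 | 35/65 |
|---|---|---|---|
| Normal, two-sided | 82.8% | 82.4% | 79.1% |
| t, 6 df, two-sided | 67.9% | 67.5% | 63.9% |
| t, 5 df, two-sided | 64.5% | 64.1% | 60.6% |
| t, 6 df, one-sided 0.05 | 81.9% | 81.6% | 78.7% |

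The two-sided effect detectable with 80% power on 6 df is 0.580, 0.582 and 0.608 SD respectively.

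**3. Error rate and power by simulation.** Logistic GEE, working independence, 2,500 runs per setting, outcome ICC 0.01 and 0.03. Assumptions that are not in the documents: a beta-binomial outcome; exposure ICC of 0, 0.1 or 0.3 (varies between women) or 1 (constant within village); village sizes all 20, 4–34 totalling 160, or 2–42 totalling 188. The effect is 0.5 log-odds per SD. The power column uses the 160-woman settings.

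| Two-sided 5% test | Predictor | False positives | Power |
|---|---|---|---|
| Uncorrected sandwich, z | woman-level | 10.5–14.9% | 84–89% |
| Kauermann-Carroll, t 6 df | woman-level | 3.5–5.8% | 62–72% |
| Mancl-DeRouen, t 6 df | woman-level | 2.6–4.3% | 51–64% |
| Uncorrected sandwich, z | village-level | 20.6–26.0% | – |
| Kauermann-Carroll, t 6 df | village-level | 7.6–9.4% | 45–56% |
| Mancl-DeRouen, t 6 df | village-level | 4.1–4.6% | 29–41% |

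A separate simulation put the lower end for the uncorrected woman-level test at about 9%. At one-sided 5%, the uncorrected test rejected a true null in about 8–10% of runs (woman-level) and 14–15% (village-level). With 188 women, the number enrolled in intervention villages before any loss, woman-level power is 69–78% (Kauermann-Carroll) or 58–71% (Mancl-DeRouen).

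**The case against.** The strongest points on the other side:

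- **The plan is silent, not wrong.** The correction sentence stands in the same paragraph, ahead of the dose-response sentences, and nothing excludes it from those models. This stands. The error inflation is therefore conditional on running them as standard GEE. But the reason the plan gives for correcting, 14 df, belongs to the arm test, and a reader following the text would not know to correct here.
- **Inflated error and low power do not coexist.** A reader might infer that one test has both up to a quarter false positives and about two-thirds power. It does not. Uncorrected, woman-level power is 84–89%, at an inflated error rate; the lower power appears only after correction.
- **Sidedness is open.** A reader might take 64–68% as the true power. That needs a two-sided test, which the sentence does not state. Table 3 is one-sided, and on that basis 79–82% would agree with the plan. Step 1 makes two-sided the likelier reading.
- **Over 20% false positives need an index constant within villages.** The checklist also records each woman's sessions, their format and duration, and the protocol reports that presentations and outreach were not consistently feasible. So this figure is an upper case for the index, and it does not apply to woman-reported exposure.
- **Other analyses do better.** Deflating n for the full ICC and also using 6 df is conservative when much of the exposure contrast lies within villages; 160 women on 6 df give 71–75%. In the same simulations, a model-based standard error gave 86–88% power with 4–7% false positives for a woman-level exposure. This stands for that predictor. For a village-level index, the model-based test rejected a true null in 7–16% of runs.
- **The analyses are exploratory.** They appear in neither Aim and are not listed endpoints. A reader might infer that they decide dissemination; the Program Evaluation section ties dissemination to cost tracking instead. This limits the priority.

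**Conclusion.** The gap is real but modest. Both within-intervention dose-response models rest on eight villages, and the plan states a small-sample correction only for the arm comparison. Without one, the two-sided false-positive rate is about 9–15% for woman-level exposure, and about 20–26% to the extent that the implementation index is constant within villages. With a 6-df reference, two-sided power at 0.5 SD is about 64–68% by noncentral t, or about 51–72% by simulation across the two corrections.

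The error rates depend on the uncorrected sandwich z-test and on the assumed village sizes and exposure ICCs. The power figures depend on the plan's own effective n of 135 (noncentral t) or its 160 women (simulation), and on two-sided testing. The documents do not settle which variance estimator or which sidedness was intended, so neither set of figures can be called the plan's actual performance.

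**What to change.** In the Data Analysis Plan:

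1. Extend the small-sample correction to both within-intervention models: a named bias-corrected sandwich variance with t on 6 df, or 5 df if village size is fitted.
2. Choose the correction with the index in mind. Of the two simulated, Mancl-DeRouen held 5% for a predictor constant within villages, and Kauermann-Carroll did not (7.6–9.4%). For woman-level exposure, Kauermann-Carroll was close to nominal and Mancl-DeRouen somewhat conservative.
3. State alpha and sidedness for these tests.
4. Restate the power sentence to match. If two-sided, 80% power is for about 0.6 SD. If one-sided 0.05 on 6 df, about 80% at 0.5 SD can stand.
5. Say which parts of the implementation index are measured per woman and which per village. Plotting the eight village rates against the village-level part would help, but replacing the test by description is a matter of preference.

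The cost is wording, wider intervals and a less favourable detectable effect. Enrolment, data collection and the primary analysis are unchanged.
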